9.7.4 Analysis of secondary outcome(s)

The secondary safety outcomes will be analyzed similar to the primary outcomes. Subgroup analyses will be conducted for selected secondary endpoints (e.g. 6 Minutes Walking Test, NYHA/WHO FC, hospitalization).

Analyses of adverse events will be conducted for PH subgroups (inoperable vs. post- surgery CTEPH patients, monotherapy vs. combination therapy PAH patients) .

Adverse events of interest will be analysed in detail. Adverse events of interest are

- Symptomatic hypotension
- Hemoptysis/ pulmonary haemorrhage

Further analyses of information on adverse events of interest as given by the detailed questionnaire and the AE page will be evaluated.

Kaplan Meier plots will describe the time until the individual events of interests

For the effectiveness variables summary statistics and changes form baseline will be calculated for

- 6 Minutes Walking Test,
- Borg Dyspnoea Index
- EO5D VAS
- Hemodynamic measurements
- Biomarkers

NYHA/WHO FC will be analyzed by frequency tables including changes from baseline.

The variables of hospitalization due to PH and drug utilization (reason and drug switch or interruption or discontinuation of Adempas®) will be analyzed by frequency tables and summary statistics.

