7 Introduction: Background and Rationale

Pulmonary Arterial Hypertension (PAH) is a rare, progressive and life-threatening disease. It is characterized by a chronic increase in pulmonary vascular resistance (PVR) due to progressive vascular remodeling that can ultimately lead to right heart failure and death [1] [2]. Symptoms of PAH are related to right heart failure and include exercise-induced dyspnea, exhaustion, leg edema and decreased quality of life. In untreated patients with idiopathic PAH the life expectancy is reduced to 2.8 years after diagnosis, whereas in contemporary registries in the era of modern PAH-specific treatments the survival rates have increased to 83% and 58% at 1 and 3 years respectively [3] [4]. The incidence is currently estimated as 2.4 cases per million adult inhabitants per year with a prevalence of 15 cases per million adult inhabitants [5]. Available PAH-specific treatments include prostacyclin analogues, endothelin receptor antagonists, and PDE5-inhibitors. The available drugs predominantly act as vasodilators and improve exercise capacity [6]. Despite advances in the clinical management

based on these available therapies for PAH, there is still significant unmet medical need for improvement as the mortality of patients with PAH remains high (15% at 1 year and 32% at 3 years) [7].

Chronic Thromboembolic Pulmonary Hypertension (CTEPH) is a different progressive and life-threatening type of pulmonary hypertension. Whereas symptoms as well as epidemiology of CTEPH are similar compared with PAH, there are significant differences regarding aetiology, diagnosis and treatment [8] [9]. In CTEPH the increase in pulmonary vascular resistance is a result of a pulmonary artery obstruction by residual organized thrombi [10]. A ventilation-perfusion-scan is important for differential diagnosis as a normal scan excludes CTEPH [11]. The standard and potentially curative treatment for CTEPH is pulmonary endarterectomy (PEA). However 20 to 40 % of patients are not eligible for surgery and in 10-15% of patients PH may persist or reoccur after surgery [12] [13] [14] [15]. Specific PAH drugs had failed in the past to show efficacy in inoperable CTEPH and before Adempas® no drug treatment has been approved for these patients [16].

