9.1 Study design

The EXPERT registry is a global, multicenter, prospective, uncontrolled, non-interventional cohort study documenting data from patients with PH treated with Adempas[®]. It is linked with the existing global COMPERA registry, a global academic multicenter prospective registry, which documents consecutive patients with the different forms of pulmonary hypertension (PH) treated with specific PAH drugs. For EXPERT the documentation in COMPERA will be extended to include additional Adempas[®]-specific data.

It is planned to include around 35 countries in the region Europe, Asia Pacific, Latin America.

The study will start after Adempas[®] has been authorized and made commercially available in the countries involved in the study.

All patients prescribed with Adempas[®] for a medically appropriate use, consent to participate, and fulfil the selection criteria are eligible for enrolment into the study. Patients will be followed up for an observation period of 1 up to 4 years (recruitment period 3 years). Patient's clinical information will be documented at time of the initial visit and approximately every three to six months according to local clinical practice thereafter. Data collection will continue until 30 days after the end of Adempas[®] therapy.

The decision on clinical management of the patient including the actual treatment duration will be determined solely by the physician.

The study ends 12 months after enrolment of the last patient

Serious adverse events will be followed up until resolution.

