9.1.1 Primary endpoint(s)

The primary endpoints are:

- Incidence of adverse events/ serious adverse events
- Incidence of all-cause mortality

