9.3.2 Variables to determine the secondary endpoint(s)

The outcome variable(s) for secondary objective(s) is/are:

- AE and SAE in the different PH indications (PAH, CTEPH)
- Adverse events of interest
 - o Symptomatic Hypotension (date BP measurement, symptoms)
 - Haemoptysis and pulmonary haemorrhage (serious and non-serious). Specific information regarding relevant history, current condition, diagnostics, treatment, specific lab values and outcome to be documented in a specific CRF section in case AE/SAE of interest occurred
- Measurements of clinical effect
 - o 6 Minutes Walking Test,
 - o NYHA/ WHO FC
 - o Borg Dyspnoea Index
 - o EQ5D VAS
 - o Haemodynamic parameters from right heart catheter measurement
 - Biomarkers
- Resource use
 - O Hospitalization (due to PH or other reason, emergency admission, intensive care unit, number of days)
 - o Outpatient visits at PH center
 - Home care (nurse, days per week, hours per day), Rehabilitation/ nursery home (days)
 - Drug use, including switch or interruption or discontinuation of Adempas[®]
 and associated reason

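### Kaplan-Meier plots for the adverse events of interest must censor event-free deaths, so read as cumulative risk they overstate it, by an amount that depends on a mortality the protocol does not give

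*Protocol*

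**What the plan says.** Section 9.7.4 names two adverse events of interest, symptomatic hypotension and haemoptysis/pulmonary haemorrhage, and fixes one time-to-event display for them: "Kaplan Meier plots will describe the time until the individual events of interests". Section 9.3.2 lists "Haemoptysis and pulmonary haemorrhage (serious and non-serious") among these events, so non-fatal cases count.

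Death belongs to neither event. Section 9.1.1 has it as a primary endpoint of its own: "Incidence of all-cause mortality". No section mentions competing risks or cumulative incidence, or says how deaths enter the curves.

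On follow-up, Section 9.1 states: "Patients will be followed up for an observation period of 1 up to 4 years (recruitment period 3 years"). Data collection stops 30 days after the end of Adempas therapy.

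On mortality, Section 7 says that "the mortality of patients with PAH remains high (15% at 1 year and 32% at 3 years"). It also reports, for idiopathic PAH in contemporary registries, that "the survival rates have increased to 83% and 58% at 1 and 3 years respectively". For CTEPH it gives no mortality figure and says only that "symptoms as well as epidemiology of CTEPH are similar compared with PAH".

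**The concern.** One minus Kaplan-Meier estimates the probability of an event in a population where the censored patients could still have it later. That is reasonable for a patient whose observation ends because the study closes. It is not for a patient who has died: a first haemoptysis or hypotensive episode can no longer happen. If such deaths are censored, the curve describes a cohort in which nobody dies, and it lies above the proportion of real patients who have the event.

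The registry exists to describe long-term safety in routine practice, and the gap widens with follow-up. The raw proportions and person-year rates of Section 9.7.3 do not show risk by a given time. The Kaplan-Meier plots are the only named display that does, for the two events singled out for detailed analysis. A prescriber who reads a 3-year risk off them would read it too high.

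**Working it through.** **Plan's own figure.** The Kaplan-Meier plan carries no number. The only design figure, 83% for at least three cases at 0.5% incidence in 900 patients (Section 9.5), reproduces as an exact binomial tail: 1 − P(X ≤ 2) = 0.827. It does not bear on this point.

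**Direction.** The protocol names no censoring rule. In a Kaplan-Meier curve for one event that excludes death, an event-free death can only be a censored observation. One minus Kaplan-Meier is then never below the Aalen-Johansen cumulative incidence, and exceeds it once events occur after such deaths. This needs no assumed rates.

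**Inputs for the size.**
- Death hazard m from Section 7: 32% at 3 years gives m = −ln(0.68)/3 = 0.1286 per year. The other survival figure, 58% at 3 years (42% dead), gives m = −ln(0.58)/3 = 0.1816.
- Lower death rates for a more stable cohort, 5 and 2 per 100 patient-years (m = 0.05 and 0.02), are assumptions.
- The event rate a is not in the protocol. A 3-year one-minus-Kaplan-Meier value of 1% to 20% is assumed, with a = −ln(1 − p)/3.

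**Formulas (constant hazards).**
- One minus Kaplan-Meier: 1 − exp(−a·t)
- Cumulative incidence: a/(a + m) × [1 − exp(−(a + m)·t)]

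**Results at 3 years with m = 0.1286.**

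| 1 − KM | Cumulative incidence | Difference (points) | Ratio |
|---|---|---|---|
| 1% | 0.83% | 0.17 | 1.20 |
| 5% | 4.16% | 0.84 | 1.20 |
| 10% | 8.33% | 1.67 | 1.20 |
| 20% | 16.71% | 3.29 | 1.20 |

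A death hazard in two pieces, matching both 15% at 1 year and 32% at 3 years, gives ratios of about 1.22 and a difference of 3.6 points at 20%.

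**How the ratio moves.**
- Time, with m = 0.1286: about 1.07 at 1 year, 1.20 at 3 years, 1.26 to 1.28 at 4 years. At an event hazard of 0.05 per year (assumed), 4-year values are 18.1% against 14.3%.
- Mortality, at 3 years: 1.28 to 1.30 with 42% dead, about 1.08 with 5 deaths per 100 patient-years, about 1.03 with 2 per 100.
- Timing: if all events fell in the first 6 months (assumption), about 1.03 even with m = 0.1286.

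**The case against.** Much can be said for the plan.

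**Legitimate method, details deferred.** Section 9.7.1 sends statistical details to the SAP, and a Kaplan-Meier curve with deaths censored is a valid cause-specific description. The error arises only when it is read as absolute risk, and the protocol does not say that it will be. This stands as a limit: the point is conditional on that reading. It does not remove the point, because the protocol itself fixes the estimator and puts no such label on the curves.

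**Supplementary role.** The analyses are descriptive and non-confirmatory (Section 9.7.1). Raw proportions and person-year rates are also planned for these events (Section 9.7.3), so no primary result depends on the plots. This stands.

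**Size.** The 32% is a PAH figure. The reference list shows that the cited registry report measures survival from time of diagnosis. Section 9.8 expects mostly prevalent and possibly more stable patients. Observation ends 30 days after therapy, so later deaths do not enter. Few patients can reach 4 years: with uniform accrual over 3 years (assumption), potential follow-up averages 2.5 years, where the ratio is about 1.17 at m = 0.1286 and about 1.06 at m = 0.05. For an event at 0.5%, the only adverse event frequency in the protocol, the 3-year difference is below 0.1 points. The 95% sampling half-width with 900 fully followed patients is 1.96 × √(0.005 × 0.995/900), or 0.46 points. All of this stands and lowers the severity.

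**Fatal events of interest.** Section 11.1 treats the cause of death as the SAE. A fatal pulmonary haemorrhage is therefore the event itself, not a competing death. This stands, and the fix must respect it.

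**Conclusion.** The point holds in a limited form. The protocol fixes an estimator that must censor event-free deaths, and a curve so built overstates cumulative risk when read that way. The direction is certain; the size is not. It rests on mortality during observation, which the protocol does not give for this cohort, on an assumed event rate, and on constant hazards. At 3 years the relative overstatement is about 20% if the cited PAH mortality applied, and about 8% or 3% under the assumed lower rates. In absolute terms, at the cited mortality, it is about 0.2 points for a 1% event and 3 to 4 points for a 20% event. Severity is minor to moderate.

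Two stronger readings are tempting, and the documents support neither. A reader might infer that this registry's curves will be a fifth to a quarter too high. That carries PAH mortality from diagnosis over to a mostly prevalent, mixed cohort, and applies the 4-year value that only the earliest enrolled can reach. A reader might also infer that the curves will contradict the raw incidence proportions because of this choice. Those proportions ignore time on treatment by definition (Section 9.7.3) while follow-up ranges from 1 to 4 years, so any time-specific estimate, Aalen-Johansen included, would differ from them.

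**What to change.** In Section 9.7.4, replace the Kaplan-Meier plots for the adverse events of interest with Aalen-Johansen cumulative incidence curves, one per event, and state that:

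- death not due to the event itself is the competing event;
- a death caused by the event counts as the event;
- administrative end of observation is censoring;
- end of treatment, with documentation stopping 30 days later, is handled by a named rule (censored, or a further competing event), because that choice also changes what the curve estimates.

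If a Kaplan-Meier version is retained, label it as cause-specific with deaths censored, so that it is not read as the proportion of patients affected.

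The cost is a few lines in the protocol or SAP and a standard procedure. The final visit already records the date of death and its relation to disease or treatment (Section 9.2.7), so no new data are needed. The reported cumulative risks will be somewhat lower than the Kaplan-Meier values.

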9.2.2 Inclusion criterion/criteria

- Female and male patients who start or are on treatment with Adempas®
- Written informed consent

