The final data collection (last visit) is 30 days after discontinuation of therapy or at end of study (whatever is earlier). At this final observation point, the patient's condition and a treatment assessment will be documented as at the follow-up visit with the additional information on:

- regular end of observation, or
- discontinuation of therapy
- reason for discontinuation, i.e.: patient failed to follow up, patient decision, investigator decision, pregnancy, insufficient / no treatment effect, unexpected strong treatment effect, (suspected) drug interaction, SAE (must be reported immediately!), death (date and relation to disease or treatment), therapy change (which therapy and reason for switch), centre closed, study termination

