9.7 Data analysis

9.7.1 Statistical considerations

Statistical analyses of this study will be of non-confirmative nature. This study is designed to support hypothesis generation.

All background variables and outcome parameters will be analyzed descriptively with appropriate statistical methods: categorical variables by frequency tables (absolute and relative frequencies) and continuous variables by summary statistics (i.e. mean, standard deviation, minimum, median, quartiles and maximum). Continuous variables will be described by absolute value and as change from baseline per analysis time point, if applicable.

All analyses will be performed for the total study population (overall analysis) and separately for PH subtype and subgroup, incident and prevalent patients, functional class at baseline, countries or regions if applicable and if patient numbers are sufficient. Prevalent patients is here defined as patients already on treatment, e.g. previously documented in the registry, whereas incident patients will be patients newly starting Adempas[®].

Patients receiving at least one dose of Adempas[®] will be included in the analysis. Whenever reasonable, data will be stratified by subgroups (e.g. age, gender).

All therapies documented will be coded using the World Health Organization – Drug Dictionary (WHO-DD). Medical history, any diseases and AEs will be coded using the latest Medical Dictionary for Regulatory Activities (MedDRA) version.

All statistical details including calculated variables and proposed format and content of tables will be detailed in the Statistical Analysis Plan (SAP). The SAP will be finalized before study database lock. The SAP is available upon request. The respective document, <7>, is listed in Annex 1.

It is planned to have at least yearly interim analysis/analyses e.g. for the purpose of the PSUR. The proportion of incident and prevalent subjects will be tracked. Analyses will refer to the primary and secondary objective. The final analysis will be performed after end of the study which is the date the analytical dataset is completely available.

All background data such as patient demographics, PH group and indication-specific characteristics and prior or concomitant medication of PH, and concomitant diseases will be described by presenting frequency distributions and/or basic summary statistics.

Sample size and disposition information by analysis time point will be displayed in a frequency table.

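### Long-term effectiveness tables will describe patients who survived and stayed on Adempas, not the enrolled cohort, and the protocol neither shows nor states this

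*Protocol*

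**What the plan says.** Section 9.7.4 states that "For the effectiveness variables summary statistics and changes form baseline will be calculated for" the 6-minute walk, Borg index, EQ5D VAS, haemodynamics and biomarkers. Functional class gets frequency tables, including change from baseline. Section 9.7.1 sets the general form: "Continuous variables will be described by absolute value and as change from baseline per analysis time point, if applicable". The protocol names no other effectiveness summary for these variables.

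The end of observation is tied to treatment. Section 9.1: "Data collection will continue until 30 days after the end of Adempas" therapy. Sections 9.2.4 and 9.2.7 repeat the 30-day limit. The reasons for discontinuation listed in section 9.2.7 include death, a change of therapy and "insufficient / no treatment effect".

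On the population, section 9.2.2 admits "Female and male patients who start or are on treatment with Adempas". Section 9.7.1 says "All analyses will be performed for the total study population (overall analysis) and separately for PH subtype and subgroup, incident and prevalent patients". It also plans a disposition table by analysis time point.

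**The concern.** Section 8.2 sets effectiveness over long-term follow-up of PH patients as a secondary objective. A mean change at year 2 or 3 will be read as answering that objective for the patients who were enrolled. Under the stated rules it can include only patients who are alive, still taking Adempas and measured in routine care. Leaving is related to outcome by the protocol's own list of reasons, so the remaining group is likely to be selected for doing well. A flat or rising curve could then come from patients with poor results leaving, with no sustained benefit in those who remain. Functional class tables share the problem: a patient who dies in class IV is not counted as a deterioration at later time points but simply disappears.

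**Working it through.** **The plan's own figure.** The protocol gives no number for effectiveness. Its one sizing calculation (section 9.5) concerns adverse events: at least three events among 900 patients at 0.5% incidence. The exact binomial value is 0.827 against the stated 83%. It reproduces but has no bearing here.

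**Step 1: who can contribute.**
- Enrolment lasts 3 years and the study ends 12 months after the last enrolment (section 9.1). Every patient could reach 1 year. Only those enrolled in the first 12 months could reach 3 years.
- Assuming even recruitment, the number eligible at 3 years is 900 × 1/3 = 300.
- These administrative limits are not attrition. The denominator must therefore be patients whose enrolment date allows the time point, not all 900.

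**Step 2: loss by death alone.** Section 7 cites PAH mortality of 15% at 1 year and 32% at 3 years.
- Maximum contributing at 1 year: 1 − 0.15 = 85%, or 0.85 × 900 = 765.
- Maximum contributing at 3 years: 1 − 0.32 = 68%, or 0.68 × 300 = 204.
- Section 7 also quotes survival of 83% and 58% at the same times, which would leave fewer.

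These figures are for PAH, not for this cohort, and say nothing direct about CTEPH.

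**Step 3: add discontinuation.** The protocol gives no rate. Assume a yearly rate d, independent of death, so that r1 = 0.85(1 − d) and r3 = 0.68(1 − d)³.

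| d (assumed) | r1 | r3 |
|---|---|---|
| 0 | 85% | 68% |
| 5% | 81% | 58% |
| 10% | 77% | 50% |
| 15% | 72% | 42% |

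**Step 4: effect on a share improved.** Suppose a share p of contributing patients has improved, and everyone who died or stopped is counted as not improved. The share in the eligible cohort is then r × p. With death alone at 3 years, any observed p is multiplied by 0.68; with d = 10% it is multiplied by about 0.50. Counting every stop as not improved gives the lower limit; the fix below counts only some reasons.

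**Step 5: effect on a mean.** A walking distance is undefined after death, so take surviving patients only. The share of survivors still on drug at 3 years is (1 − d)³. The observed mean exceeds the mean in all survivors by [1 − (1 − d)³] × D, where D is the difference in mean change between continuing and stopped patients.
- d = 5%: 0.143 × D, which is 2.1, 4.3 or 8.6 m for D = 15, 30 or 60 m.
- d = 15%: 0.386 × D, which is 5.8, 11.6 or 23.2 m.

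Both d and D are assumed. If D is zero there is no bias in the mean among survivors; if D is negative the direction reverses.

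**Step 6: does the protocol already cover this?** Section 9.7.6 names survivor bias and refers to section 9.8. That section deals with the interval between diagnosis and recruitment, that is, with selection at entry. It does not mention loss during follow-up. Splitting new starters from existing users does not help, because new starters who fail also leave.

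**The case against.** The strongest reply is that nothing here is mis-stated. Section 9.7.1 calls the analysis non-confirmative and hypothesis-generating, the design is uncontrolled, and observed change on drug is a legitimate description in an exposure registry. Patients who leave are also reported: all-cause mortality is a primary endpoint, reasons for discontinuation are tabulated in section 9.7.4, disposition is shown by time point, and a final visit records the patient's condition. Statistical detail belongs to the SAP and missing-data handling to the Data Management Plan (section 9.7.7).

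Much of this stands. It makes the point one of presentation and interpretation for a secondary objective. But the other tables report who left without altering the effectiveness summary. A final-visit value is taken near the time of stopping and does not appear at later time points. Death and stopping for lack of effect are outcomes, not data gaps to be queried. And section 9.8 is protocol text that discusses one form of survivor bias and omits this one.

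A reader might also infer that existing users' baseline is an on-treatment value, so that the pooled change is diluted in proportion to their share. The inference is understandable: effectiveness variables are collected at the initial visit, and only blood pressure is requested by name from before the first dose. The documents do not establish it:
- Baseline is not defined, and the SAP may define it.
- Section 9.3 allows historic data from records, and section 9.7.1 says "Prevalent patients is here defined as patients already on treatment, e.g. previously documented in the registry", so pre-dose values may exist.
- Section 9.7.1 already plans a separate new-starter analysis, so any dilution is confined to the overall table.
- The share of existing users is not given. The large majority of prevalent cases in section 9.8 refers to disease, not to Adempas use.
- A proportional dilution requires no further change in existing users. With half the cohort existing users, the pooled change is 50% of the new-starter change under that assumption, but 63% if existing users still change by a quarter as much (0.5 + 0.5 × 0.25 = 0.625).

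**Conclusion.** The point holds for attrition on treatment. The stop rule and the observed-change summary together mean that long-term effectiveness tables describe survivors still on drug. The direction is favourable to Adempas provided leavers do worse than stayers, which the listed reasons for leaving make plausible but do not prove. The only bound from the protocol's own figures is that at most 85% at 1 year and 68% at 3 years would contribute if cohort mortality matched the cited PAH mortality; discontinuation lowers this by an unknown amount. No corrected effect in metres can be derived, because effect size, discontinuation rate and the outcome of leavers are all absent. The documents also do not support a claim that the pooled estimate is diluted by a known factor, or that the pooled table must be dropped. This is a cheap improvement to a descriptive secondary analysis. It does not affect the primary safety objective.

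**What to change.** In section 9.7.4:
- At each time point, use as denominator all patients whose enrolment date allows that time point.
- In the functional class change tables, add separate categories for died, stopped Adempas (by reason), and on drug but not assessed.
- For walking distance, report beside the observed mean the share improved. Count death, and stopping for insufficient effect or change of therapy, as not improved. Show other stopping reasons and patients not assessed separately. The SAP should fix the threshold for improvement in advance.
- State that observed mean changes apply to patients continuing on drug.
- Read change from baseline mainly from the new-starter analysis already planned in section 9.7.1. The overall table may stay, labelled as mixing new starters with existing users whose baseline may be on treatment.

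In section 9.8, add loss of patients during follow-up through death or stopping as a limitation, beside the existing text on prevalent entry.

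Cost: analysis wording and extra table rows. Date of death and reason for discontinuation are already collected (section 9.2.7), so no new data are needed. The drawback is busier tables and a less favourable displayed effect. Requiring pre-dose values for existing users, or excluding those without one, would be a different matter: the first is additional data collection and the second adds a selection step, so neither is part of this fix.

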9.1.2 Secondary endpoint(s)

The secondary endpoints are:

Safety

- Incidence of AE and SAE in the different PH indications (PAH, CTEPH)
- Incidence of AE of interest overall and in the different PH indications (PAH, CTEPH)

Effectiveness

• Clinical effect in the follow-up of PH patients

Resource use

- Hospitalization / outpatient visits
- Administration and any change in drug treatment for PH

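### Section 9.7.4 narrows the declared hospitalisation endpoint to admissions due to PH and states no time denominator, although follow-up varies from under 1 year to 4 years

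*Protocol*

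**What the plan says.** **What is declared.** Section 9.1.2 lists "Hospitalization / outpatient visits" under resource use, with no restriction to PH. Section 9.3.2 spells the variable out as "Hospitalization (due to PH or other reason, emergency admission, intensive care unit, number of days" and adds "Outpatient visits at PH center" and "Home care (nurse, days per week, hours per day), Rehabilitation/ nursery home (days", along with drug use.

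**What is analysed.** The dedicated sentence in Section 9.7.4 covers "The variables of hospitalization due to PH and drug utilization", and these "will be analyzed by frequency tables and summary statistics". Earlier in the same section, hospitalisation appears without the PH restriction, as an example of an endpoint for subgroup analysis.

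**How long patients are observed.** Section 9.1 says: "Patients will be followed up for an observation period of 1 up to 4 years (recruitment period 3 years". Section 9.2.7 can shorten this: "The final data collection (last visit) is 30 days after discontinuation of therapy or at end of study (whatever is earlier".

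**How other events are handled.** Section 9.7.3 reports adverse events, serious adverse events and deaths both as a raw proportion, which it describes as ignoring time on treatment, and as a rate per person-year. Section 9.7.4 carries that approach over to the secondary safety outcomes and adds Kaplan-Meier plots for the events of interest. Neither is extended to resource use.

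**The concern.** There are two separate problems.

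First, the sections disagree on what the endpoint is. The declared variable is admission for any reason, with the reason recorded. The analysed variable is admission due to PH. Section 9.7.4 uses both forms within itself. Whoever writes the tables cannot tell whether the headline figure is all-cause or PH-attributed, and the outpatient and home care components have no dedicated analysis text.

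Second, admissions accumulate with time under observation. Follow-up here depends on enrolment date and on when treatment stops. A mean count or a share ever admitted, taken without regard to observation time, mixes the admission rate with the length of follow-up. Section 9.7.1 plans breakdowns by PH subtype, by incident and prevalent patients and by country or region, and at least yearly interims that refer to the secondary objectives. Groups or data cuts with longer follow-up would appear to use more hospital care even at an identical rate, and patients who stop early would look like low users.

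**Working it through.** The protocol gives no figure for hospitalisation or resource use, so there is nothing of its own to reproduce on this point. Its one sample-size figure, 83% for at least three events at 0.5% incidence in 900 patients, reproduces (exact binomial 82.7%) but has no bearing here.

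**Inputs from the protocol:** 3-year recruitment; 1 to 4 years of follow-up for patients who stay on treatment; observation ending 30 days after stopping.

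**Assumptions, because the protocol gives no values:** a constant admission rate *r* of 0.1, 0.2 or 0.4 per patient-year; uniform accrual; a discontinuation hazard of 0 to 0.3 per year.

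**Step 1. Same rate, different follow-up.** With Poisson counts over *t* years, the mean count is *r·t* and the share with at least one admission is 1 − exp(−*r·t*).

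| r | Mean, 1 y | Mean, 4 y | Ratio | Share, 1 y | Share, 4 y | Ratio |
|---|---|---|---|---|---|---|
| 0.1 | 0.10 | 0.40 | 4.0 | 9.5% | 33.0% | 3.5 |
| 0.2 | 0.20 | 0.80 | 4.0 | 18.1% | 55.1% | 3.0 |
| 0.4 | 0.40 | 1.60 | 4.0 | 33.0% | 79.8% | 2.4 |

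The ratio of means is 4/1 whatever the rate. The ratio of shares depends on the rate. A patient observed for one month at *r* = 0.2 has a mean of 0.2/12 = 0.017.

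**Step 2. Yearly data cuts.** With uniform accrual over 3 years and no discontinuation, mean follow-up of those enrolled is 0.5, 1.0 and 1.5 years at the first three yearly looks and 2.5 years at the end. At *r* = 0.2 the mean counts are 0.10, 0.20, 0.30 and 0.50, a fivefold rise (2.5/0.5) with no change in rate.

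**Step 3. Early stopping.** Follow-up was simulated as uniform on 1 to 4 years, cut at discontinuation plus 30 days, with *r* = 0.2.

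| Discontinuation hazard per year | Mean follow-up (y) | Under 1 year | Share ever admitted | Mean count |
|---|---|---|---|---|
| 0 | 2.50 | 0% | 38.4% | 0.50 |
| 0.1 | 2.20 | 8.8% | 34.4% | 0.44 |
| 0.2 | 1.95 | 16.8% | 31.0% | 0.39 |
| 0.3 | 1.75 | 24.1% | 28.1% | 0.35 |

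The share ever admitted falls by about 10 percentage points although the admission rate never changes.

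**Step 4. With a time denominator.** Admissions divided by patient-years gives 0.20/1 = 0.20 and 0.80/4 = 0.20, so the comparison is no longer distorted. The form of the rate matters. Section 9.7.3 divides the number of *patients* with events by person-time. If person-time is not stopped at the first event, that form gives 0.181/1 = 0.18 at 1 year and 0.551/4 = 0.14 at 4 years, so it would not fully remove the dependence. For a repeatable event such as admission, the numerator should be admissions.

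**The case against.** **The components are covered elsewhere.** A reader might infer from 9.7.4 that non-PH admissions, outpatient visits and home care go unanalysed. The protocol does not support that. Section 9.7.1 promises a descriptive analysis of every outcome parameter, and 9.7.4 itself mentions hospitalisation without restriction for subgroups. What remains is an unexplained narrowing and an inconsistency between sections.

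**Drug harm would be missed.** A reader might also infer that restricting to PH-attributed admissions hides admissions caused by the drug. This largely fails. Under Section 11.1 an adverse event leading to hospitalisation is serious, apart from listed exceptions (planned stays, stays under 12 hours, normal treatment or monitoring of the disease, routine right heart catheterisation). Serious adverse events get person-year rates in 9.7.3, and haemoptysis and symptomatic hypotension get closer analysis still.

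**The denominator belongs in the SAP.** The method as worded does not rule out annualised summaries, and 9.7.1 leaves calculated variables and table content to the SAP. That has force: silence alone would be no finding. But the protocol does set person-time for one class of event and a method without it for another with the same unequal follow-up, and its own sections disagree on the variable.

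**Summaries might be per visit or window.** Resource use is recorded at each visit, and per-window figures would not grow with total follow-up. This stands in part. Section 9.2.7 fixes no visit dates and expects gaps of 3 to 6 months, so at a constant rate a count between visits still varies twofold (6/3), and patients who leave within a window are only partly observed.

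**Conclusion.** The point holds, with modest impact. Section 9.7.4 analyses a narrower hospitalisation variable than 9.1.2 and 9.3.2 declare, and it gives no time denominator although 9.7.3 does so for adverse events.

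Mean counts would differ fourfold between 1 and 4 years of follow-up at any constant rate. The share ever admitted would differ by a factor of about 2.4 to 3.5 for assumed rates of 0.4 down to 0.1 per year. These sizes rest on a constant rate and on admission and discontinuation rates that the protocol does not give. Follow-up under 1 year is inferred from the 30-day rule; the protocol does not state it.

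It would go too far to conclude that the endpoint merely reflects length of follow-up: an unadjusted count still carries the admission rate, mixed with exposure. No hypothesis test or sample-size figure depends on this variable, and the study is uncontrolled and descriptive. The practical harm is misleading comparisons between subgroups, countries and successive interim reports.

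**What to change.** In Section 9.7.4:

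- Name the variable as in 9.1.2 and 9.3.2: all-cause hospitalisation split by PH and other reason, plus outpatient visits and home care or rehabilitation.
- Alongside the planned frequency tables, report admissions and hospital days per patient-year of observation, showing total person-time and number of patients. Count admissions in the numerator, and use observation time in the denominator so that it matches the period over which admissions are recorded.
- Use the same format for subgroups and for the yearly interims.

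Time to first admission could be added but is optional. The cost is a few sentences and a few more tables. Admission reasons, hospital days and observation dates are already collected, so no new data item is needed.
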